We hypothesize that Myrbetriq™, as a $\beta(3)$ -AR agonist⁶, could harbor a great therapeutic potential for controlling storage bladder symptoms (LUTS) and ureteral pain associated with ureteral stent placement.

Study Objective and Endpoints

The objective of this pilot study is to assess whether Myrbetriq™ will improve post-operative ureteral pain and discomfort, reduce bladder storage symptoms and increase quality of life following ureteral stenting. This study will be conducted as an exploratory pilot investigation. In doing so, we will confirm the potential effect size for reduction in associated pain following stenting within this study population. Results from this pilot study will also be used to assess feasibility for the design and conduct of a larger, prospective study in this population.

Primary Endpoints:

- Improvement from baseline in the Incontinence Symptom Severity Index (ISSI) in the Myrbetriq™ group at the 1 week follow-up and 2 week follow-up compared to placebo group.
- Improvement from baseline in the number micturition per 24 hours and the number of incontinence episodes in the Myrbetriq™ group at the 1 week follow-up and 2 week follow-up compared to placebo group.

Exploratory Endpoints:

- Improvement in pain and discomfort perception using a 10 point Visual Analog Scale for pain assessment (VAS) at the 1 and 2 week follow-up.
- Improvement from baseline on the Patient Global Impression of Severity (PGI-S) at the 2 week follow-up.

- Reduction in pain medicine intake at the 2 week follow-up.

Study Methods

This study is a prospective, randomized, double-blind, placebo-controlled 2 week clinical trial to evaluate the efficacy of Myrbetriq™ to reduce ureteral stent related pain and bladder symptoms in subjects undergoing a urologic procedure involving ureteral stenting. The study will be conducted at Southern Illinois University (SIU) School of Medicine, Department of Urology and its affiliated hospitals in Springfield, IL.

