Subjects will be enrolled per the inclusion/exclusion criteria. Subjects will be screened and consented prior to their stent placement procedure for stone disease. Patients will be formally enrolled and randomized post-operatively based on no severe complications intra-operatively, such as extensive extravasation, hematoma could confound the pain and compromise the results. All subjects will complete at baseline and all follow-up visits: 1) the Incontinence Symptoms Severity Index (ISSI), 2) American Urologic Association symptom score (AUASS) 3) the Visual Analog Scale (VAS) to represent change in acute pain 4) the Patient Global Impression of Severity (PGI-S) quality of life scale 5) a voiding diary for 1 to 3 days preceding day, 7, and stent removal visits, and then 14 days after the stent removal (if done by day 28) to obtain base line diary and 6) a narcotic log starting after surgery through 14 days after stent removal (if done by day 28). The ISSI will be used to assess any change in voiding symptoms. This scale has been validated to efficiently capture and quantify urological symptoms⁷. The voiding diary is used to capture the number of micturition per day, urgency and associated incontinence. The VAS has been validated to measure changes in acute pain that are clinically significant⁸. The PGI-S has been proven to efficiently summarize a patient's perception to change in severity in regards to lower urinary tract symptoms (LUTS)⁹. Subjects will undergo a blood draw prior to stent placement (complete blood count (CBC), comprehensive metabolic panel (CMP) and urine analysis (sugar, protein, WBC/RBC, bacteria)) to verify eligibility. These laboratories will not be repeated if they were performed routinely as a part of preoperative work up. 100 subjects will be equally randomized into 1 of 2 study groups, active treatment with Myrbetriq™ or administration of a placebo. A daily 50 mg dose of Myrbetriq™ will be administered in the treatment group for up to 4 weeks initiated on the day of stent placement. A 50mg dose was chosen as the initial dose due to the acute nature of the symptoms which do not require long term therapy. It has been shown that Myrbetriq™ 50 mg taken orally once daily has superior efficacy in treatment of LUTS when compared to placebo by week 4 (the duration of this study) and this effect was maintained. A 50mg dose was proven to be safe and effective to patients in Phase III trials^{10,11}. Both study groups will receive similar prescriptions of narcotics in dose and number. Patients will be given a log to record use of narcotics. If a different form of narcotics is prescribed due to side effects or allergic reaction, a narcotic analgesia converter calculator will be used to adjust for the doses, for analysis purposes. Post-operative symptoms and pain medicine intake will be assessed at days 1, 7 via telephone interview, and with a clinic visit the day of stent removal (or day 14 if stent removal postponed) and via phone 14 days after the stent is removed. If patient is to have stent removed on day 28, or later, the patient will receive a day 21 telephone call to obtain post-operative pain and pain medicine intake, as well as questionnaires. They will remain on study drug until day 28. Use of prescription, over-the-counter and supplemental medications for pain control will be captured using self-report and direct observation/recording of medication labels by the study team. These interviews will be conducted by study staff who will be blinded to the subject's treatment. Subjects will complete

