
the ISSI, the AUASS, voiding diary, VAS, narcotic log, and PGI-S during these follow ups. The day 14 assessments will be collected prior to their stent removal procedure.

Study Subjects

Patients will be identified and recruited through the SIU urology clinics and St. John's Hospital during a 24 month enrollment period. Participation in this study will be completely voluntary. Male and female subjects presenting with planned stent placement for ureteral obstruction or post-ureteroscopy procedures for stone, except for those undergoing uteropelvic junction obstruction, will be evaluated for participation. Should the patient decline to participate, their choice will not change their prescribed course of standard urologic treatment. After review and approval by the local Institutional Review Board, the study will enroll 100 patients that meet the inclusion criteria below and agree to participate. Annually, the study investigators perform approximately 350 stenting procedures (based on 2 previous years of clinical data).

Inclusion Criteria

1. Age \geq 18.
2. Subject scheduled to undergo a ureteral stent placement for ureteral obstruction or post-ureteroscopy procedure.
3. Otherwise healthy subjects who are able and willing to participate in the study.
4. None of the planned interventions are documented in the labeled contraindications, warnings and precautions of the study drug.

Exclusion Criteria

1. Does NOT give consent.
2. Subject is using prohibited medications which cannot be stopped safely at the screening visit. Subject is excluded if using restricted medications not meeting protocol-specified criteria:
 - (i) Phytotherapy for BPH or a 5-alpha reductase inhibitor within 3 months, with persistent urinary symptoms and AUASS more than 7.
 - (ii) Taken an oral alpha agonist, anticholinergic or cholinergic medication within 5 days of the first screening visit with the following exception(s): a singular dose given in ER or on the hospital floor prior to procedure, topical anticholinergic eye drops used for glaucoma or inhaled anti-cholinergic used for COPD.
 - (iii) Taken tricyclic antidepressants within 2 weeks of the first screening visit.
 - (iv) Taken an estrogen, androgen, or any drug producing androgen suppression, or anabolic steroids within 3 months with the following exceptions: any topical creams for local treatment.
3. Post void residual volume $>$ 350 mL.

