19. Unable to follow protocol directions due to organic brain or psychiatric disease.
20. Intra-operative complications that require hospital admissions.
21. History of alcoholism or any other substance abuse, which, in the opinion of the investigator, would affect compliance with the protocol.

Assessment or Procedure	Baseline/ Stent Placement	Post-Op Day 1 (phone)	Post-Op Day 7 (phone)	Stent removal (Post-Op Day 14 if stent not removed) visit	Post- Op Day 21 (phone) (if stent not removed)	2 weeks after stent removal or Day 42 (phone)	Early Withdrawal
Informed Consent	X						
Verify Eligibility	X						
Review Medical & Surgical History	X						
Physical Examination (H & P)	X			BP and HR only			BP and HR only
Review Prior & Current Medications	X	X	X	X	X	X	X
Review Adverse Events		X	X	X	X	X	X
ISSI	X	X	X	X	X	X	X
VAS	X	X	X	X	X	X	X
PGI-S Quality of Life Scale	X	X	X	X	X	X	X
AUASS	X	X	X	X	X	X	X
Voiding diary			X	X		X	
Pain log		X	X	X	X	X	X
Laboratory screening tests (hematology & chemistry)	X						
Randomization	X						
Study drug administration/Accountability	X			X		X only if you have drug	X

Visit window for all visits are +/- 2 days

Study Procedures

Informed Consent

All participants will be required to provide written informed consent. The study staff will introduce the study after being informed the subject is potentially eligible. The study coordinator and/or study staff will review the informed consent document with the subject. The subject will be provided information related to the study purpose, procedures, potential risks and benefits to participation, voluntary nature of their potential participation and provide them an opportunity to ask and have answers to all questions prior to obtaining any signature. A study investigator will be available to answer any questions. Subjects will not be compensated for participation and there are no additional costs to subjects for participation in the study.

Randomization Schema

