Data analysis will be concluded upon the completion of the study. Subjects' age, height, weight, and other continuous baseline variables will be summarized using descriptive statistics, while gender, race and other categorical variables will be provided using frequency tabulations. Medical history data will be summarized using frequency tabulations by system organ class and preferred term. Chi-square and t-tests will be used, as appropriate, to compare percent change and mean change from baseline in the ISSI, voiding diary, narcotic log, VAS score and PGI-S at the final study visit (14 days) or at any early termination visit. A split-plot ANOVA with repeated measures will be used for each measure (ISSI, VAS and PGI-S) to compare groups (Myrbetriq™ and placebo) over time and to determine if there is an interaction between groups. Significance will be assumed when $p < 0.05$. A preliminary power analysis based on previously published data, using an estimated SD for each study group of 4.17, a sample size of 50 in each study group (Myrbetriq™ and placebo) has an 80% power to detect an ISSI difference of 25% between the two groups with a significance level (alpha) of 0.05 (two-tailed)¹².

Pertinent to each Specific Aim are the following calculations:

- Primary Endpoints: Comparison of the change from baseline in ISSI and voiding diaries between Myrbetriq™ and placebo will be made using an independent t test for continuous scoring and a chi-squared test for ordinal scoring. Inferential analyses of changes from base line in micturition episodes per 24 hours and incontinence episodes per 24 hours will be performed using a stratified rank analysis to compare to baseline and as a covariance for each treatment.
- Exploratory Endpoints: Comparison of the change from baseline of total VAS between Myrbetriq™ and placebo will be made using an independent t test for continuous scoring and a chi-squared test for ordinal scoring. Comparison of the change from baseline in PGI-S between Myrbetriq™ and placebo will be made using an independent t test for

continuous scoring and a chi-squared test for ordinal scoring. Comparison of pain medicine intake between Myrbetriq™ and placebo groups will be made using an independent t test.

Safety Considerations

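### The 2-week test counts an early-termination value from any day as a day-14 value, and for the voiding diary that branch of the rule has no scheduled data

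*Combined protocol and SAP*

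**What the plan says.** The primary endpoints are ISSI and the diary counts of micturitions and incontinence episodes, each assessed "at the 1 week follow-up and 2 week follow-up compared to placebo group" (Study Objective and Endpoints).

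Under Statistical Analyses, the general paragraph compares change from baseline in ISSI, "voiding diary, narcotic log, VAS score and PGI-S at the final study visit (14 days) or at any early termination visit". A split-plot ANOVA follows for ISSI, VAS and PGI-S, with no list of visits. The Primary Endpoints bullet then gives a t test (chi-squared if ordinal) for ISSI and the diaries and a stratified rank analysis for the diary counts. It names neither a day nor early termination.

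On timing, Study Methods has telephone contacts on days 1 and 7, then continues "with a clinic visit the day of stent removal (or day 14 if stent removal postponed". It adds: "The day 14 assessments will be collected prior to their stent removal procedure". For late removals: "If patient is to have stent removed on day 28, or later, the patient will receive a day 21 telephone call" and "They will remain on study drug until day 28".

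The schedule of assessments has one column, "Stent removal (Post-Op Day 14 if stent not removed) visit", a window of 2 days either side for every visit, and a last contact headed "2 weeks after stent removal or Day 42 (phone". Its Early Withdrawal column marks ISSI, VAS, PGI-S, AUASS and the pain log, but not the voiding diary.

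**The concern.** A result labelled week 2 should describe patients at about day 14. The rule lets in a termination value from any day. If symptoms change between day 7 and day 14, and more patients leave one arm than the other, that difference in timing looks like a treatment effect. If leaving is balanced but the drug effect is still growing, the contrast is diluted. The pilot is meant to supply an effect size for a larger trial, so a mistimed contrast would be carried forward. For the diary, the rule calls for a value that the schedule does not collect.

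**Working it through.** **Which values can enter the week-2 test**

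- *Early termination.* The rule names it and sets no earliest day. The 2-day window governs when visits take place; nothing says that it limits which values are tested.
- *Early stent removal.* The visit that supplies the week-2 value falls on the removal day, or on day 14 if the stent is still in. No earliest removal day is given, and no separate day-14 assessment is scheduled for a stent already out. A removal before day 12 (14 - 2) would therefore supply an off-window value. This follows from the schedule but is not stated. Assessments precede removal, so the issue is timing only.
- *Diary.* It is scheduled at day 7, at stent removal/day 14 and two weeks after removal. Patients who reach the removal/day-14 visit have one; early terminators have none scheduled.
- *Other analyses.* By-visit summaries do not separate the cases if a visit means a schedule column, because removal and day 14 share one. The split-plot ANOVA leaves out the diary and names no visits.

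**Base for the illustration**

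The plan gives 50 per arm, SD 4.17, two-sided alpha 0.05 and 80% power for a 25% ISSI difference. With no reference mean, the 80% can be neither confirmed nor refuted. The standard error of a difference is 4.17 × √(2/50) = 0.834. The difference giving 80% power is (1.960 + 0.842) × 0.834 = 2.34 points, or 2.36 with the t distribution. That equals 25% only if the reference mean is 2.36/0.25 = 9.44.

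**Unequal early termination, no true effect** (assumed: 15% v 5%, leaving at random, day-7 value substituted)

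False shift = (0.15 - 0.05) × change from day 7 to day 14.

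- 2-point change: 0.10 × 2 = 0.2. In standard errors, 0.2/0.834 = 0.24. Type I error ≈ P(Z > 1.72) + P(Z < -2.20) = 0.043 + 0.014 = 5.7%.
- 4-point change: 0.10 × 4 = 0.4. In standard errors, 0.4/0.834 = 0.48. Type I error ≈ P(Z > 1.48) + P(Z < -2.44) = 0.069 + 0.007 = 7.7%.

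A simulation (6,000 runs per case; days 1, 7 and 14; SD 4.17 at each; correlation 0.5) gave shifts of 0.20 and 0.41 and type I error of 6.0% and 8.0%. A mixed model on the same data gave shifts of 0.00 and 0.01 and type I error of 5.1% and 5.0%.

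**Equal rates, half the effect at day 7** (assumed)

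Contrast = 2.36 × (1 - 0.5f), where f is the fraction of off-day values.

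| f | Contrast (points) | Dilution | Power by formula | Simulated power, current rule | Simulated power, mixed model |
|---|---|---|---|---|---|
| 10% | 2.24 | 5% | 76% | 77% | 77% |
| 20% | 2.12 | 10% | 71% | 71% | 73% |
| 30% | 2.01 | 15% | 66% | 67% | 68% |

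The mixed model restores the estimate (2.37 to 2.38 points) but hardly any power.

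**Leaving depends on the unseen day-14 score** (15% v 5%, log-odds 1 per SD, no true effect, 2- or 4-point change)

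- Mixed model: shift -0.25 or -0.23, type I error 6.4% or 5.7%.
- Current rule: shift +0.05 or +0.26, type I error 5.5% or 6.0%.

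Which is closer to the truth depends on the size and direction of the time trend.

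**The case against.** The best defence is that this is an exploratory pilot with mainly descriptive analysis. The Primary Endpoints bullet does not repeat the substitution, and the value before removal is a reasonable endpoint when the visit is tied to removal. Much of this stands and limits the point. It does not remove it: the general paragraph includes ISSI and the diary in the substitution, sets p < 0.05, and does not say how it relates to the bullet.

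Several stronger readings are tempting, and the documents do not support them:

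- *The rule cannot be applied to the diary at all.* Only the early-termination branch fails.
- *The rule costs up to 14 points of power (80% to 66%).* Nearly all of that comes from having no day-14 value. The mixed model loses almost as much.
- *Post-removal values contaminate week 2.* The plan collects the assessments before removal.
- *Early removals are common.* No rate is given. The word postponed in Study Methods suggests that day 14 is the expected removal day, although the schedule leaves earlier removal open.
- *Withdrawal after day 14 creates two competing values.* The sentence calls day 14 the final visit, so early termination most naturally means before it. A short clarification is enough.
- *Early removal is ordinary missing data.* Once the stent is out, an on-stent day-14 symptom does not exist. What to estimate then is a choice of question.
- *The mixed model is always better.* It is not when leaving depends on the unseen score.

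**Conclusion.** The point holds. As written, a termination value from any day is tested as a day-14 value, and for the diary that branch has no scheduled data. The same mistiming from stent removal before day 12 is a firm inference from the schedule, not a stated fact.

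The size is unknown. Under the assumed 15% v 5% random termination, the false shift is about 0.2 or 0.4 ISSI points and type I error about 6% or 7-8%. Under equal rates with half the effect at day 7, the contrast is diluted by 5-15% for 10-30% off-day values. The termination rates, time trends and day-7 effect are all assumptions, and the 2.36-point base is solved from the stated power. The textual defect does not depend on them. Severity is modest, but the rule should be settled before unblinding so that the choice cannot follow the results.

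**What to change.** 1. For ISSI and VAS, and PGI-S if scored as continuous, make the week-1 and week-2 comparisons from one mixed model for repeated measures in all randomised patients. Use values at days 1, 7 and 14, with baseline as covariate, treatment, visit, treatment-by-visit and unstructured covariance. State that it replaces the early-termination substitution, the split-plot ANOVA and the t test for these measures.
2. Assign each value by its actual post-operative day, with the protocol's own 2-day window: days 5-9 for day 7 and days 12-16 for day 14. An early-termination value enters only the window in which it falls.
3. Treat early stent removal separately from withdrawal. State whether the week-2 question is symptoms at day 14 with the stent in, or the last value before removal up to day 14. Report the other as a sensitivity analysis, and give the distribution of removal days by arm.
4. Keep the current rule as a sensitivity analysis, limited to terminations before day 14, because missing at random can fail (about 0.25 points off in the case above).
5. Analyse the diary at days 7 and 14 without early-termination substitution and report the number missing by arm. Its post-removal baseline is a separate matter. Analyse the narcotic log as intake per day on study through day 14, so that shorter follow-up does not count as lower use.
6. Reconcile the description of day 14 as the final visit with the schedule's last contact, and with the 2-week and 4-week durations that both appear in Study Methods.

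The cost is SAP wording, a window table and a standard model, with no new visits or data. The downsides are a little more analysis work and reliance on missing at random. The gain is a correctly timed estimate, not more power.

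### The label for the efficacy test visit conflicts with the schedule, and the repeated-measures ANOVA has no visit list

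*Combined protocol and SAP*

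**What the plan says.** Statistical Analyses compares change from baseline in ISSI, voiding diary, narcotic log, VAS and PGI-S by t and chi-square tests "at the final study visit (14 days) or at any early termination visit". It adds a split-plot repeated-measures ANOVA of ISSI, VAS and PGI-S "to compare groups (Myrbetriq™ and placebo) over time and to determine if there is an interaction between groups". No list of visits is given for that ANOVA.

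The other sections give these time points:

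- Study Objective and Endpoints sets the primary comparisons "at the 1 week follow-up and 2 week follow-up compared to placebo group".
- Study Methods opens by calling the study a "placebo-controlled 2 week clinical trial", then gives active treatment "for up to 4 weeks initiated on the day of stent placement".
- Study Methods ends follow-up "via phone 14 days after the stent is removed". The schedule of assessments heads that column "2 weeks after stent removal or Day 42 (phone".
- Study Methods also says: "The day 14 assessments will be collected prior to their stent removal procedure".
- The schedule collects ISSI, VAS and PGI-S at every contact from baseline to the last call. The Day 21 call applies only when the stent has not been removed.

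**The concern.** The objective concerns symptoms that follow stenting, and the primary endpoints are at weeks 1 and 2. In the schedule, post-operative day 14 is not the final contact. The final contact is itself normally 14 days after an event, namely stent removal. Both words of the label, final and 14 days, can therefore be attached to either assessment. While that is open, two analysts could test different visits, or the visit could be settled after the data are seen.

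For the diary the difference is sharp. Study Methods uses the diary taken 14 days after stent removal as the baseline diary, and the schedule shows no diary at the baseline visit. A change from baseline at that contact would compare the reference diary with itself.

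The ANOVA has a related gap. Nothing in the text excludes baseline, Day 21 or the last call. Baseline precedes the drug, and the last call normally follows stent removal, so neither is informative about an on-stent drug effect. Averaging them into the group main effect pulls a real on-stent difference toward zero. A classical split-plot analysis also needs complete rows: with Day 21 included it loses everyone whose stent is already out, and one missed call loses a subject. The pilot is meant to supply an effect size for a larger trial, so a diluted or selectively based estimate carries forward.

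**Working it through.** **1. Which assessment is the final visit?** For post-operative day 14: the two-week description, the week-1 and week-2 endpoints, and the statement that day 14 data are taken before removal. In the schedule, the stent-removal/day-14 column is also the only scheduled column after baseline headed as a visit and not as a phone contact. For the last call: it is the last contact in the schedule, and Study Methods dates it 14 days after removal. The first reading is better supported, but Statistical Analyses does not settle it.

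**2. The plan's own figure.** Inputs from Statistical Analyses: 50 per group, SD 4.17, two-sided alpha 0.05, 80% power, a 25% ISSI difference. No reference mean is given, so 25% cannot be turned into points and the 80% cannot be confirmed directly. Solving backwards:

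- Standard error = 4.17 × √(2/50) = 0.834.
- Normal approximation: (1.960 + 0.842) × 0.834 = 2.34 points. With the noncentral t it is 2.36 points.
- Implied reference mean = 2.34/0.25 to 2.36/0.25, about 9.3 to 9.4.

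The 2.36 points are used below as the single-visit effect with 80% power.

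**3. ANOVA group main effect.** Assumptions not in the documents: the effect is 2.36 points on the on-stent days and zero at baseline and after removal; the SD is 4.17 at each contact; the correlation ρ between contacts is equal, 0.3 to 0.7.

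- SD of a subject's mean over k contacts = 4.17 × √((1 + (k − 1)ρ)/k).
- Days 1, 7, 14 at ρ = 0.5: 4.17 × √(2/3) = 3.40. Standard error 3.40 × 0.2 = 0.681. Ratio 2.36/0.681 = 3.47. Power 93%.
- Adding the post-removal contact: average effect 2.36 × 3/4 = 1.77. SD 4.17 × √(2.5/4) = 3.30. Standard error 0.659. Ratio 2.68. Power 76%.

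**4. Interaction.** Noncentrality λ = 25 × Σ(δₜ − mean)²/(4.17² × (1 − ρ)). With days 1, 7, 14 and post-removal at ρ = 0.5: Σ = 3 × 0.59² + 1.77² = 4.18, so λ = 25 × 4.18/8.69 = 12.0 on 3 and 294 degrees of freedom. Power 84%.

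| Contacts included | Average effect | Main-effect power, ρ = 0.3 / 0.5 / 0.7 | Interaction power, ρ = 0.3 / 0.5 / 0.7 |
|---|---|---|---|
| Days 1, 7, 14 | 2.36 | 97 / 93 / 88% | 5% (effect constant) |
| Days 1, 7, 14, post-removal | 1.77 | 86 / 76 / 67% | 68 / 84 / 97% |
| Baseline, days 1, 7, 14, post-removal | 1.42 | 72 / 58 / 49% | 85 / 95 / 99.8% |
| Days 7, 14 | 2.36 | 94 / 90 / 86% | 5% (effect constant) |

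**5. Share due to the post-removal contact.** At ρ = 0.5, dropping only that contact from the five-contact set moves main-effect power from 58% to 76%. If day 1 also had no effect, the five-contact average would be 2.36 × 2/5 = 0.94 points with 30% power, and dropping the post-removal contact would bring it to 43%.

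**The case against.** The best defence is that the label is loose but its meaning can be recovered. The two-week description, the endpoint times and the pre-removal collection of day 14 data all point to the stent-in-place assessment. This largely stands. A reader might infer that the t and chi-square tests are fixed at a stent-free call, with power near alpha; the documents do not support that.

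The second defence is that the ANOVA text does not say that all contacts enter. That is correct: the full visit set is one permitted reading, not a stated rule. The gap is that no set is stated.

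Third, keeping baseline as a level of a split-plot analysis is ordinary practice, with treatment read from the interaction, which the plan also tests. In the five-contact case that test has at least 85% power, and at ρ of 0.5 and above it has more power than a main effect on days 7 and 14. This stands as far as power goes. It does not supply a directional on-stent estimate. The planned t tests and by-visit summaries partly do, once their visit is named.

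Fourth, the study is an exploratory pilot that relies mainly on descriptive statistics. This lowers the stakes, but the plan still sets a significance threshold and aims at an effect size.

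**Conclusion.** The point holds as a matter of specification: the test visit carries a label that conflicts with the schedule, and the ANOVA has no visit set. It is worth correcting before analysis.

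The size is conditional. If the post-removal contact is averaged with days 1, 7 and 14, the main effect falls by a quarter, from 2.36 to 1.77 points. Its power falls from 93% to 76% at correlation 0.5 (97% to 86% at 0.3, 88% to 67% at 0.7). This rests on the assumed 2.36-point effect, equal correlations, a constant on-stent effect and none after removal. The interaction is not diluted.

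Two further inferences go too far:

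- **A fall from 90% to 30% power caused by the post-removal call.** Most of that contrast comes from adding baseline and a day 1 assumed to have no effect.
- **The studied condition is always gone at the last contact.** Study Methods allows removal on day 28 or later. With Day 42 as the alternative date, some subjects could be less than 14 days past removal, or still stented.

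**What to change.** In Statistical Analyses:

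1. Replace the label for the t and chi-square tests with the stent-in-place assessment as the schedule defines it: the stent removal visit, with data taken before removal, or post-operative day 14 if the stent is not removed.
2. Replace the split-plot ANOVA with a mixed model for ISSI, VAS and PGI-S on the week-1 and week-2 on-stent assessments. Use baseline as a covariate and report the group difference at each visit. A missing visit then does not remove the subject.
3. Report Day 21 and the post-removal/Day 42 contact separately as descriptive summaries.
4. Reconcile the two-week description of the trial with the treatment period of up to four weeks and the later calls, so that final visit has one meaning throughout.

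The cost is wording in the analysis section, with no new data. The small downside is that the later contacts become descriptive, as does day 1 unless it is added to the model as a further on-stent visit.

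### The split-plot ANOVA for ISSI, VAS and PGI-S drops subjects with any missing time level and leaves sphericity unaddressed; a mixed model on visits due for everyone would avoid both

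*Combined protocol and SAP*

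**What the plan says.** Statistical Analyses plans, for three outcomes: "A split-plot ANOVA with repeated measures will be used for each measure (ISSI, VAS and PGI-S". Its purpose is "to compare groups (Myrbetriq™ and placebo) over time and to determine if there is an interaction between groups", which I read as a group-by-time interaction test, judged at p < 0.05. The section does not list the time levels. For this analysis it gives no missing-data rule, covariance assumption, sphericity check or epsilon correction.

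Study Methods and the schedule of assessments collect all three measures at baseline, day 1, day 7, the stent-removal visit (day 14 if removal is postponed), and a last call two weeks after removal or at day 42. There is also a conditional contact. Study Methods says: "If patient is to have stent removed on day 28, or later, the patient will receive a day 21 telephone call". The schedule labels the column "Post- Op Day 21 (phone) (if stent not removed". Three of the four follow-ups due for everyone are by telephone, and the schedule has an early-withdrawal column.

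The primary ISSI comparison is a separate independent t-test. The t and chi-square tests are tied to the 14-day visit or an early-termination visit. The power statement, "has an 80% power to detect an ISSI difference of 25% between the two groups", is for a two-group comparison.

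**The concern.** Two properties of the classical split-plot ANOVA fit this schedule poorly.

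First, it needs a full row of data per subject. One missed questionnaire removes the subject from every visit, including those where the data exist. A subject not due a day-21 call has that cell empty by design.

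Second, the F test for group-by-time has its nominal error rate only if all pairwise differences between time levels have equal variance (sphericity). The contacts run from stent placement, through closely and then widely spaced stented contacts, to a call after removal. Constant correlation across them is a strong assumption.

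The ANOVA is the only named inferential analysis that runs over time. The primary endpoint is set at week 1 and week 2, and the pilot is meant to confirm an effect size for a larger study. A longitudinal estimate from a depleted subset, or an interaction p-value that is too small, would feed into that design. The ANOVA and the t-tests could also cover different subjects for the same outcome.

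**Working it through.** **Inputs from the documents.** 50 subjects per arm, SD 4.17, two-sided alpha 0.05, 80% power and a 25% ISSI difference (Statistical Analyses); contact times (Study Methods and the schedule of assessments).

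**Assumptions.** Missed-contact rate *m* per follow-up, independent between contacts; within-subject covariance. The documents give neither.

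**1. The plan's own figure.** The standard error of a two-group difference is 4.17 × √(2/50) = 0.834. The difference detectable with 80% power is (1.960 + 0.842) × 0.834 = 2.34 points, or 2.36 by the noncentral t distribution. The 25% therefore implies a reference ISSI mean of about 9.35 to 9.44, which the plan does not state. The 80% is reproduced only under that reading, and it is the power of a two-sample t-test, not of the ANOVA.

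**2. Complete cases.** The share of subjects with every follow-up is (1 − *m*)^*k* for *k* follow-ups, taking baseline as always present.

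| Time levels after baseline | k | m = 5% | m = 10% |
|---|---|---|---|
| Day 7, day 14 | 2 | 0.95² = 90% | 0.90² = 81% |
| Day 1, day 7, removal/day 14, last call | 4 | 0.95⁴ = 81% | 0.90⁴ = 66% |

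If day 21 is added as a level, every subject not due that call is excluded whatever *m* is. The documents do not say what share that would be.

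**3. Interaction test.** Type I error of the uncorrected group-by-time F test was simulated with no treatment effect, 50 complete subjects per arm and 8,000 runs per setting. The Monte Carlo standard error is √(0.05 × 0.95 / 8,000) = 0.24 percentage points. Decaying correlation means ρ^(days apart/7), with ρ = 0.5, 0.7 or 0.9.

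| Contacts entered | Compound symmetry | Decaying correlation (epsilon) |
|---|---|---|
| Baseline, 7, 14 | 5.5% | 5.9-6.1% (0.82-0.93) |
| Baseline, 1, 7, 14 | 5.2% | 7.4-8.1% (0.56-0.65) |
| Baseline, 1, 7, 14, 28 | 5.2% | 7.0-8.4% (0.51-0.68) |
| Baseline, 1, 7, 14, 21, 42 | 4.6% | 7.2-9.4% (0.47-0.68) |

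Two intermediate patterns gave 5.4-5.8% (part constant, part decaying correlation) and 5.9-6.4% (constant correlation, unequal variances). With a Greenhouse-Geisser correction, every setting fell between 4.4% and 5.5%. The group main effect stayed at 4.7-5.3% throughout, because it compares subject means and does not use the sphericity assumption.

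**The case against.** The strongest reply is that this is a secondary analysis in a pilot described as mainly descriptive, and that the primary endpoint does not depend on it. That stands. The ISSI comparison is an independent t-test, and the section allows an early-termination value in its tests. A missed day-1 call does not remove a subject from it.

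It follows that one tempting inference is unsupported. A reader might put the complete-case numbers (about 41 or 33 per arm with four follow-ups) into the two-sample formula at 2.36 points and conclude that the planned 80% power drops to 72% or 62%. Those figures apply a t-test formula to the ANOVA's surviving subjects. They are neither the power of the planned t-test nor that of the interaction test.

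The second reply is that the time levels are not stated. If only baseline, day 7 and day 14 are entered, the losses and the inflation are at the low end of the ranges, and day 21 plays no part. This also stands, and it is why no single figure can be given.

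The third reply concerns sphericity. A reader might infer that the schedule itself breaks it, so that the interaction p-value is certainly too small. The documents do not show that. Sphericity is a property of the covariance, not of the visit spacing. Under compound symmetry the same contacts give about 5%, and the plan does not rule out a correction.

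What the reply does not remove is that the named method discards collected data and relies on a condition left unaddressed, when a standard alternative needs neither.

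**Conclusion.** The point holds as a fault in the choice of longitudinal method, of moderate weight. The plan should be changed, but the primary comparison is not invalidated.

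The deletion follows from the method. Its size depends on an assumed miss rate and on which levels are entered: 10% to 34% of subjects lost across the settings in the first table. Entering day 21 would change the population to subjects whose stent stays in. The inflation is conditional: none under compound symmetry, and roughly 6-9% against a nominal 5% under decaying correlation, with the larger values only when more contacts than baseline, day 7 and day 14 are entered.

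A reader might also infer that the complete-case estimate is materially biased. That is possible if missing a contact depends on earlier symptoms, but the documents give no dropout rate or mechanism from which to size it.

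**What to change.** Replace the split-plot ANOVA with a likelihood-based mixed model for repeated measures for ISSI, VAS and PGI-S:

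- terms for treatment, visit and treatment-by-visit, with unstructured covariance;
- all available data at the visits due for every subject, so that a missed contact does not delete the rest;
- day 21 summarised separately, for those who receive that call;
- drug-placebo contrasts at week 1 and week 2 reported with 95% CIs, matching the stated primary endpoint times.

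The cost is one paragraph of analysis text and slightly more programming, with no new data. The model assumes that missing values are missing at random given the observed data, and the plan should say so.

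If the ANOVA is kept, limit its time levels to baseline, day 7 and day 14 and apply a Greenhouse-Geisser correction. That deals with the error rate and the day-21 gap, but incomplete subjects would still be deleted.
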